#### **ARIA related intervention algorithm**

The tables below detail the ARIA-E linked intervention algorithm based on these scores (Table 1 and Table 2) and the intervention algorithm for ARIA-H microhemorrhage (Table 3) and superficial siderosis (Table 4). Algorithms are based on definite ARIA findings only. For ARIA-E, the algorithm relies on measures of the largest diameter of any ARIA-E. For ARIA-H, areas of microhemorrhage are counted and larger areas of hemorrhage (macrohemorrhage) are noted. Should both, ARIA-E and ARIA-H be present in the same subject, the more conservative procedure should be followed.

For ARIA cases where there are symptoms that are possibly related to the ARIA findings, more stringent procedures should be considered (e.g., withhold treatment for symptomatic cases even if the procedures in the table would not require it).

**Table 1 Procedures for Asymptomatic ARIA-E**

Number of New Occurrences	Dose Adjustment	MRI Monitoring
Any new individual lesions $\leq$ 2 cm	Appropriate actions should be discussed among the site PI, DIAN-TU Medical Director, and PAL	Every 4 weeks until stable
Any new individual lesions $>$ 2 cm	Follow the Symptomatic ARIA-E guidance	Follow the Symptomatic ARIA-E guidance

 Based on new definite ARIA findings (excluding baseline incidences)

**Table 2 Procedures for Symptomatic ARIA-E: Any incidence of symptomatic ARIA-E or asymptomatic with lesions  $>$ 2 cm**

Step-wise Response	Dose Adjustment	MRI Monitoring
Initial action	Suspend/hold dosing	Every 4 weeks until stable
Once symptoms and ARIA-E deemed stable	Appropriate actions should be discussed among the site PI, DIAN-TU Medical Director, and PAL	Consider additional MRI(s) depending on the size, and presence of symptoms. Subsequent MRI monitoring should continue per protocol unless agreed otherwise by PI, PAL, and Medical Director
If no new MRI findings after dosing restart and MRI	Appropriate actions should be discussed among the site PI, DIAN-TU Medical Director, and PAL	Resume MRI monitoring per protocol

Note: Asymptomatic lesions  $>$  2 cm are based on measurements of new definite ARIA findings

**Table 3 Procedures for ARIA-H Microhemorrhage**

Number of New Occurrences (Cumulative)	Dose Adjustment	MRI Monitoring
10-15 new, cumulative occurrences	Appropriate actions should be discussed among the site PI, DIAN-TU Medical Director, and Project Arm Leader (PAL)	Consider additional MRI monitoring until stable
> 15 new, cumulative occurrences	Appropriate actions should be discussed among the site PI, DIAN-TU Medical Director, and PAL	MRI 4 weeks later, consider additional MRI monitoring until stable, then continue monitoring per protocol unless agreed upon otherwise by the PI, Medical Director, and PAL

 Based on new definite ARIA findings (excluding baseline incidences)

**Table 4 Procedures for Superficial Siderosis**

Number of New Occurrences	Dose Adjustment	MRI Monitoring
≥ 1 new occurrence of superficial siderosis	Appropriate actions should be discussed among the site PI, DIAN-TU Medical Director, and Project Arm Leader (PAL).	Consider additional MRI(s) depending on the size and presence of symptoms. Subsequent MRI monitoring should continue per protocol unless agreed otherwise by PI, PAL, and Medical Director

 Based on new definite ARIA findings (excluding baseline incidences)

### 1.15 Drug-specific Discontinuations or Withdrawal

Subjects will be discontinued from the study if they had a prolonged acute infusion reaction that was not rapidly responsive to symptomatic medication such as antihistamines, nonsteroidal anti-inflammatory drugs, and/or narcotics and/or brief interruption of infusion. Mild infusion reactions responding to treatment or requiring pretreatment before subsequent infusions would not require discontinuation, unless discontinuation was considered appropriate based on medical judgment of the principal investigator or Medical Director.

Following the approval of Amendment 7, the dose escalation process will begin. If the investigator considers that a subject may not be a candidate for dose escalation for any reason, the investigator should contact the sponsor to discuss whether to discontinue the subject.

## 2 STUDY DRUG

### 2.1 Drug Description

The active product or placebo will be supplied in a 20 mL vials for preparation with the appropriate diluent for intravenous infusion. Details for supplies will be provided in the *Pharmacy Manual*.

### 2.2 Drug Treatment Regimen

This study was initiated as a comparison of solanezumab (400 mg administered as an intravenous infusion of approximately 70 mL) compared to placebo. The active drug group was given an intravenous infusion of solanezumab 400 mg Q4W.

The study protocol was amended to increase the dose administered up to 1600 mg Q4W; following approval of Amendment 7, the dose-escalation process will begin (which includes signing a new ICF). After receiving at least two doses at the 400 mg level, 4 weeks ( $\pm$  4 days) apart, subjects should receive at least two doses at the 800 mg dose level, 4 weeks ( $\pm$  4 days) apart, before proceeding to the 1600 mg dose level. Changes in dosage may be made in the event of ARIA as described in section 1.14 or for other safety reasons at the investigator's discretion with notification of a Medical Director, PAL, or designee.

In addition to the Solanezumab Schedule of Visits, additional assessments during the dose escalation period are required, as described in the dose escalation study schedule. The first doses of 800 mg will be given at the DIAN-TU site or a medically qualified facility, such as an infusion clinic, until blinded safety results are evaluated for the first 20 subjects (active or placebo) to receive an 800 mg dose infusion (Table 5); subsequent doses may be given by a home health nurse. After the safety evaluation, first doses of 800 mg for the remaining subjects may be given by a home health nurse, if deemed appropriate (Table 6).

Similarly, the first doses of 1600 mg will be given at the DIAN-TU site or a medically qualified facility such as an infusion clinic until blinded safety results are evaluated for the first 20 subjects (active or placebo) to receive a 1600 mg dose infusion (Table 5). After this evaluation, first doses of 1600 mg for the remaining subjects may be given by a home health nurse, if deemed appropriate (Table 6).

All subjects will have a 1-hour post dose monitoring period after their first 800 mg and first 1600 mg doses.

Subjects will continue dosing for up to a minimum of 204 weeks and a maximum of 360 weeks based upon when the subject was randomized into the study.

**Table 5** DIAN-TU-001 Solanezumab Schedule of Visits: Dose Escalation Period (At least 20 Subjects for Each Dose Level)

PROCEDURE:	Dose (mg)	800	800	sMRI	1600	1600	1600	1600
	VISIT SITE	DIAN-TU a	H	MRI	DIAN-TU a	H	H	H
	Dose Escalation Timing (weeks) b	0	4	5	8	12	16	20
Informed Consent	X							
Vital Signs	X	X			X	X	X	X
12-Lead ECG		X				X		
3T Safety MRI c				X				
Drug-specific Testing d	X	X			X	X		X
Hematology, Chemistry, Urinalysis		X				X		
Study Drug Administration (800 mg) e	X	X						
Study Drug Administration (1600 mg) f					X	X	X	X f
1-Hour Post-Infusion Monitoring	X				X			

**Footnotes:**

- a The first dose of 800 mg and the first dose of 1600 mg for each subject will be given at the DIAN-TU site or a medically qualified facility such as an infusion clinic until blinded safety results are evaluated for the first 20 subjects (active or placebo) to receive escalated dose infusions. After this evaluation, first doses of 800 mg and 1600 mg may be given by a home health nurse, if deemed appropriate.
- b Because subjects will begin dose escalation at different visits, timing indicates weeks relative to the first dose of 800 mg.
- c Safety magnetic resonance imaging (MRI) will be done at the DIAN-TU site or at a qualified imaging center in reasonable proximity to the subject's home for those not close to their DIAN-TU site. When possible, these will be done at an ADNI and/or ADCS site qualified imaging center. Safety MRIs must be conducted at least 5 days before escalating dose to 1600 mg so results of the central read can be reviewed by the site before the escalation.
- d Drug-specific tests include testing for plasma A $\beta$  and other biomarkers, solanezumab levels and anti-solanezumab antibodies. These labs may be drawn more frequently if treatment emergence of immunogenicity is detected. Samples for plasma solanezumab levels should be collected before infusion and within 30 min after completion of infusion for post-dose levels.
- e Infusion occurs after all other procedures at each visit.
- f Dosing at 1600 mg every 4 weeks to continue through the duration of the study.

**Table 6 DIAN-TU-001 Solanezumab Schedule of Visits: Dose Escalation Period  
(Remaining Subjects for Each Dose Level After Safety Evaluation and Clearance)**

PROCEDURE:	Dose (mg)	800	800	sMRI	1600	1600	1600	1600
	VISIT SITE a	H	H	MRI	H	H	H	H
	Dose Escalation Timing (weeks) b	0	4	5	8	12	16	20
Informed Consent	X							
Vital Signs	X	X			X	X	X	X
12-Lead ECG		X				X		
3T Safety MRI c				X				
Drug-specific Testing d	X	X			X	X		X
Hematology, Chemistry, Urinalysis		X				X		
Study Drug Administration (800 mg) e	X	X						
Study Drug Administration (1600 mg) f					X	X	X	X f
1-Hour Post-Infusion Monitoring	X				X			

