22. The first dose of 800 mg and the first dose of 1600 mg for each subject will be given at the DIAN-TU site or a medically qualified facility such as an infusion clinic until blinded safety results are evaluated for the first 20 subjects (active or placebo) to receive escalated dose infusions. After this evaluation, first doses of 800 mg and 1600 mg may be given by a home health nurse, if deemed appropriate.
23. Site study coordinators should call subjects either during or within two weeks after V3, V4 and V5. For V6 and subsequent home visits, coordinator calls can be made with less frequency at the discretion of the PI or designee, and/or coordinator, and subject, but should occur at least every 3 months.
24. PET imaging studies may be omitted if visit due to early termination (ET) and occurs less than 6 months after the previous PET imaging or if precluded by local regulations/dosimetry limits. In the event of ET, other procedures may also be eliminated on a case-by-case basis, as determined by the sponsor.
25. See section 1.12 for details of drug-specific test samples at the ET visit.
26. Study drug administration only if subject is continuing double-blind treatment beyond year 4.

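### Appendix 4 states the solanezumab rule for moving first escalated doses to the home in two ways: two evaluations, one per dose level, in section 2.2, but a single evaluation releasing both levels in three footnotes

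*Protocol*

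**What the plan says.** Appendix 4, section 2.2 (Drug Treatment Regimen) keeps first 800 mg infusions at a trial site or medical facility "until blinded safety results are evaluated for the first 20 subjects (active or placebo) to receive an 800 mg dose infusion". It then sets a parallel condition for the higher dose: first 1600 mg infusions stay there "until blinded safety results are evaluated for the first 20 subjects (active or placebo) to receive a 1600 mg dose infusion". The release is tied to that second review: "After this evaluation, first doses of 1600 mg for the remaining subjects may be given by a home health nurse", again where this is judged appropriate.

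The table titles in the same section take the same line. Table 5 is headed "Dose Escalation Period (At least 20 Subjects for Each Dose Level", and Table 6 is for the "Remaining Subjects for Each Dose Level After Safety Evaluation and Clearance".

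Table 5 footnote a reads differently. It names both first doses, holds them at the facility "until blinded safety results are evaluated for the first 20 subjects (active or placebo) to receive escalated dose infusions", and continues: "After this evaluation, first doses of 800 mg and 1600 mg may be given by a home health nurse, if deemed appropriate". The same sentences stand as footnote 22 of the 4-year double-blind schedule and as footnote 8 of the schedule beyond year 4.

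**The concern.** The rule decides when a subject's first infusion at a higher dose may leave a medical facility. Section 2.2 gives each dose level its own cohort of 20 and its own evaluation. The footnotes have one cohort, not tied to a dose level, and one evaluation that opens the home setting for both levels.

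A site following the footnotes could give a first 1600 mg infusion at home at a point where section 2.2 would not yet allow it. Section 1.13.2 of the appendix says that infusion reactions usually begin during or shortly after the infusion, so the place of the first infusion is a safety matter. Two of the three footnotes sit under the main visit schedules, away from the table titles that would steer the reader to an evaluation per level.

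**Working it through.** No sample size, power or error rate is involved, so the check sets the passages side by side and follows the Table 5 timetable.

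**Inputs**

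| Place in Appendix 4 | Cohort evaluated | What it releases to the home |
|---|---|---|
| Section 2.2, 800 mg | first 20 subjects given 800 mg | first 800 mg doses |
| Section 2.2, 1600 mg | first 20 subjects given 1600 mg | first 1600 mg doses |
| Table 5 and 6 titles | at least 20 per dose level; clearance per dose level | Table 6 schedule for the remaining subjects |
| Table 5 footnote a; schedule footnotes 22 and 8 | first 20 subjects given escalated infusions, level not stated | first doses of 800 mg and 1600 mg together |

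**Step 1, number of evaluations.** Section 2.2: 2. Footnotes: 1, since both levels are released by the same evaluation.

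**Step 2, order of doses.** The arm began at 400 mg, so 800 mg is itself an escalated dose. Table 5 places the first 800 mg infusion at week 0, the second at week 4, the safety MRI at week 5 and the first 1600 mg infusion at week 8. The gap between the two first doses is 8 − 0 = 8 weeks.

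**Step 3, possible readings of the footnotes.**

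- *Any escalated dose counts.* A subject enters the cohort at week 0. The evaluation can then be finished with as few as 0 subjects given 1600 mg; section 2.2 requires 20.
- *A subject counts only after both levels.* A subject enters the cohort at week 8. There is still one evaluation, and on the Table 5 timetable first 800 mg doses are released 8 weeks later than under section 2.2.
- *Each level is evaluated in turn.* This agrees with section 2.2, but the footnotes do not say it.

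Two of the three readings conflict with section 2.2, in opposite directions.

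**Step 4, how far the count can fall.** Under the first reading, 0 is reached only if the 20th subject has had 800 mg and the evaluation is finished before the earliest subject reaches week 8. With slower entry into escalation, some of the 20 would already have had 1600 mg, so the count lies between 0 and 20. Section 2.2 and the footnotes give neither the pace of entry nor the time the evaluation takes.

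**Step 5, scope.** Table 5 lists six infusions. Two carry the location condition (weeks 0 and 8); the other four (weeks 4, 12, 16 and 20) are already placed at home. The condition therefore covers first doses only.

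**The case against.** The best reply is that a careful reader would reach the right conclusion anyway. Section 2.2 is the full statement of the rule, and it is explicit about 1600 mg. Both table titles speak of each dose level. The dose-escalation row to which footnotes 22 and 8 belong sends the reader to Tables 5 and 6. Footnote a names the two first doses before it mentions the evaluation, so it can be taken as shorthand for one evaluation per level. This stands in part: the misreading is less likely than the footnotes alone suggest. It does not remove the conflict, because the shorthand appears three times and refers to a single evaluation.

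Other safeguards do not depend on the wording. Every subject has at least two 800 mg doses before 1600 mg, an MRI reviewed before 1600 mg, and one hour of monitoring after each first escalated dose. Staff who give study drug must be trained and equipped for allergic reactions (main protocol, section 6.1.13). These limit the consequence but do not settle where the first dose may be given.

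Few first escalated doses may also remain. Section 1.5 of the appendix describes the increase to 1600 mg in the past tense, and main protocol section 6.3.5 expects double-blind visits to end by November 2019. The protocol does not say when the evaluations were completed, and footnote 8 belongs to the schedule for years 5 to 7.

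Three stronger readings may tempt a reader, and the protocol does not support them:

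- *That the footnotes dispense with a 1600 mg evaluation.* They never say so. They leave it open.
- *That 20 is too few because placebo subjects count.* Counting active and placebo subjects together is stated the same way in all four places, so it is a consistent choice. The number on active drug among the 20 cannot be derived without assuming how the estimated 72 non-carriers were divided between the arms.
- *That infusion reactions rise with the single dose.* Section 1.13.2 does not say this. Section 1.6 reports reactions in 3 of 8 subjects at 10 mg/kg (about 700 mg) and calls them apparently mild and self-limited.

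**Conclusion.** The contradiction holds. One operative safety rule is given as two evaluations of 20 subjects, one per level, in section 2.2, and as one evaluation of 20 in Table 5 footnote a and schedule footnotes 22 and 8. Its size is the number of subjects evaluated at 1600 mg before first 1600 mg doses may be given at home: 20 under section 2.2, and anywhere from 0 to 20 under the footnotes as worded. The lower end assumes that any escalated dose counts towards the 20 and that the evaluation is finished within the 8-week gap in Table 5.

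This is a matter of conduct and safety oversight, limited to first doses at each level. It does not touch the efficacy analysis or power. It is worth correcting because it bears on subject safety and the correction is small.

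**What to change.** Reconcile section 2.2, Table 5 footnote a, footnote 22 of the 4-year schedule and footnote 8 of the schedule beyond year 4, so that all four state the same rule. The text should say whether the 800 mg and 1600 mg evaluations are separate, which subjects count towards the 20 for each, and which first doses each evaluation releases. If the rule differs from the titles of Tables 5 and 6, the titles need the same edit. Which rule applies is for the sponsor's medical team to decide.

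The cost is a change to a few sentences in Appendix 4 and a notice to sites and home nurses. No assessment, analysis or sample size changes.

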**Footnotes:**

- a Infusions and safety visits (designated as occurring at home [H]) may occur at the DIAN-TU site or, for subjects who live at a distance from the DIAN-TU site, these visits may be conducted by a trial-designated home health nurse at the subject’s home or other trial-identified location. These visits may include phone calls from the host DIAN-TU site staff.
- b Because subjects will begin dose escalation at different visits, timing indicates weeks relative to the first dose of 800 mg.
- c Safety magnetic resonance imaging (MRI) will be done at the DIAN-TU site or at a qualified imaging center in reasonable proximity to the subject’s home for those not close to their DIAN-TU site. When possible, these will be done at an ADNI and/or ADCS site qualified imaging center. Safety MRIs must be conducted at least 5 days before escalating dose to 1600 mg so results of the central read can be reviewed by the site before the escalation.
- d Drug-specific tests include testing for plasma A $\beta$  and other biomarkers, solanezumab levels and anti-solanezumab antibodies. These labs may be drawn more frequently if treatment emergence of immunogenicity is detected. Samples for plasma solanezumab levels should be collected before infusion and within 30 min after completion of infusion for post-dose levels.
- e Infusion occurs after all other procedures at each visit.
- f Dosing at 1600 mg every 4 weeks to continue through the duration of the study.

Study drug arms that demonstrate a potential clinical benefit may have an open-label extension period. Eligible subjects may be offered the opportunity to receive active drug for up to 2 years in an open-label extension. During OLE, subjects could receive an intravenous infusion of solanezumab 400 mg up to 1600 mg once every 4 weeks.

All subjects enrolled in the open-label extension for solanezumab will start at the 400 mg dose level. After receiving 400 mg every 4 weeks ( $\pm$  4 days) for at least 2 infusions, subjects will be titrated to the 800 mg dose level. After receiving 800 mg every 4 weeks ( $\pm$  4 days) for at least 2 infusions, subjects will be titrated to the 1600 mg dose level. After 2 doses at the 1600 mg dose level, a safety MRI will be performed. If MRI findings prior to dosing in the OLE warrant more frequent MRIs during the dose escalation period of the open-label extension, the PI may request for review and approval by the sponsor medical monitoring team. Please refer to Table 7 for a detailed schedule of dose-titration in OLE.

Changes in dosage may be made in the event of ARIA as described in section 1.14 or for other safety reasons at the investigator’s discretion with notification of a Medical Director or designee.

**Table 7 DIAN-TU-001 Solanezumab Schedule of Visits: Dose Escalation Period in the Open-label Extension Period**

PROCEDURE:	Dose (mg)	400	400	800	800	1600	1600	sMRI
	VISIT	OLE V1	OLE V2	OLE V3	OLE V4	OLE V5	OLE V6	MRI
	Dose Escalation Timing (weeks)	0	4	8	12	16	20	21
	Informed Consent	X						
	Verification of Eligibility for OLE	X						
	3T Safety MRI a	X						X
	Study Drug Administration (400 mg)	X	X					
	Study Drug Administration (800 mg)			X	X			
	Study Drug Administration (1600 mg) b					X	X	

**Footnotes:**

a Safety MRI(s) will be done at the DIAN-TU site or at a qualified imaging center in reasonable proximity to the subject’s home (MRI) for those not close to their DIAN-TU site. When possible, these will be done at an ADNI and/or ADCS site qualified imaging center.

b Dosing at 1600 mg every 4 weeks to continue through the duration of the study.

**2.3 Packaging, Preparation and Administration of Study Drug**

The investigator or designee is responsible for administering the investigational agent to the subject, verifying that instructions are followed properly, maintaining accurate records of study drug dispensing and collection, and returning all unused study drug to the sponsor’s designee at the end of the study.

Materials and Supplies

The site or trial-designated home health nurse will be provided vials containing 400 mg/20 mL of solanezumab or placebo. The vials should be stored at 2°C to 8°C (36°F to 46°F). Normal sterile saline solution (0.9% sodium chloride) will be used for dilution and as placebo in the control subjects.

For each 400 mg dose, the content of 1 vial will be diluted with 50 mL sodium chloride intravenous infusion (0.9%) for a resulting infusate of 400 mg IP/70 mL.

For each 800 mg dose, the contents of 2 vials will be diluted with 200 mL sodium chloride intravenous infusion (0.9%) for a resulting infusate of 800 mg IP/240 mL.

For each 1600 mg dose, the contents of 4 vials will be diluted with 200 mL sodium chloride intravenous infusion (0.9%) for a resulting infusate of 1600 mg IP/280 mL.

Additional details are provided in the *Pharmacy Manual*.

Before infusion, the diluted solution should be inspected visually for particulate matter or discoloration. If particulate matter or discoloration are present, the solution should NOT be used and new product should be dispensed for use via IWRS. A product complaint form should be completed and submitted to the sponsor and the concerning vial quarantined pending further instruction. Refer to the *Pharmacy Manual* and *Global Manual of Operations* for procedures for reporting problems with drug preparation and for requesting a replacement dose. After each intravenous bag is prepared, it will be identified as a dose of study drug without identification of the drug or dose. Once prepared, the infusate solution should be stored at room temperature for a total of no more than 6 hours.

Clinical study materials will be labeled according to the country's regulatory requirements.

All study staff will be instructed to contact the investigator as soon as possible if he or she has a complaint or problem with the study drug so that the situation can be assessed. If particulate matter is seen in the vial or the prepared solution, a product complaint form needs to be completed and submitted to the sponsor or designee within 24 hours. The investigator or his/her designee is responsible for handling the following aspects of the product complaint process in accordance with the instructions provided for this study (see the *Pharmacy Manual* or *Global Manual of Operations* for additional details):

- Recording a complete description of the product complaint reported and any associated AEs using the study-specific complaint forms provided for this purpose
- Faxing the completed product complaint form within 24 hours to the sponsor or its designee
- If the investigator is asked to return the product for investigation, he/she will return a copy of the product complaint form with the product

